11.1.1 CT Scan Progression of Non-measurable Lesions

Progression will be defined based on PCWG-3 and RECIST 1.1 as all other lesions, including small lesions (longest diameter <10 mm or pathological lymph nodes $10- <15$ mm short axis) as well as truly non-measurable lesions. All non-measurable lesions should be recorded at baseline. Measurements are not required and these lesions should be followed as “present”, “absent”, or in rare cases, “unequivocal progression.” Multiple non-measurable lesions involving the same organ should be recorded as a single item on the case report form (e.g., ‘multiple enlarged pelvic lymph nodes’ or ‘multiple liver metastases’).

11.2 Symptomatic Skeletal Related Events

Time to first occurrence of SSE will be defined as the time from randomisation to documentation of any of the following (whichever occurs first) + 1 day:

- Use of external beam radiation therapy to relieve bone pain
- Occurrence of new symptomatic pathological bone fractures that may be vertebral or non-vertebral. Asymptomatic compression fractures detected by radiology review only will not be considered a SSE.
- Spinal cord compression
- Change in antineoplastic therapy to treat bone pain
- Surgical intervention to treat bone pain

Adverse event, concomitant medication, concomitant treatment, or survival follow-up CRFs and the participant’s medical record will be the source of these findings and presented as categorical data.

11.3 Analgesic/Opiate Use

Analgesic/opiate use will be assessed via BPI-SF, the WHO analgesic scale, and medical record review at entry

with a lead-in period (<28 days). The WHO analgesic scale will be completed every three cycles (based on medical review) and questionnaires will be administered every three cycles until month 24, and yearly thereafter.

11.4 Metabolic Biomarkers

Initial investigations will focus on analysis of biomarkers at selected time points; it is envisioned that additional funding will be acquired for investigation of additional time points.

Inflammatory and cytokine systemic milieu: Serum/plasma aliquots (baseline and cycle 6) from all Arm A and B patient samples are intended for interrogation of a panel of markers associated with inflammation including IL1 β , IL-2, IL-6, TNF α and adiponectin. These samples may be run in single or multiplex reactions as appropriate using a commercial platform such as MesoScale Diagnostics. Results from these investigations will be correlated with c-reactive protein and measured outcomes of exercise response and disease progression.

Insulin/Glucose Metabolism: Serum aliquots (baseline and cycle 6) from all Arm A and B patient samples are intended for assessment of insulin levels by e.g. enzyme-linked immunosorbent assay (ELISA). Insulin sensitivity will be calculated using these fasting serum insulin values and plasma glucose determinations obtained in the additional clinical blood assessments, where the HOMA-IR method will be applied. C-peptide will also be assessed in all samples and used to monitor glucose levels longitudinally in both the intervention and control groups. Additional assays for IGF-1 will also be performed.

Androgen biosynthesis: Serum aliquots from all Arm A and B patient samples at baseline are intended for assessment of androgen levels (Testosterone, DHT, androstenedione, DHEA, 17-hydroxyprogesterone, 17-hydroxypregnenolone and progesterone) levels by mass spectrometry (MS). Previous studies using this assay have demonstrated results in a lower limit of quantitation of 1 pg per sample for testosterone and DHT, respectively. Intra-assay coefficients of variation generated using human serum for high-, mid-, and low-range samples were 3.5%, 3.1%, and 3.8% for testosterone and 6.3%, 4.3%, and 15.8% for DHT, respectively.

11.5 Physical Function

Physical function will be assessed using strength assessments (1RM), a cardiopulmonary exercise test (CPET) and a functional performance test (400m walk). Strength assessments will be quantified in kilograms lifted, and will be dependent upon the location and size of bone metastatic lesions present as to which tests are performed (Chest Press, Leg Press, Seated Row and Leg Extension). All strength assessments should be attempted if not contraindicated. Cardiopulmonary exercise capacity will be quantified by VO₂peak (L.min and mL/(kg.min)) and workload achieved (watts) during a successful CPET (RPE \geq 9). Functional performance will be represented by time (in seconds) taken to perform a 400m walk test.

11.6 Quality of Life

Symptoms will be considered independently of other outcome measures. Pain will be assessed via BPI-SF and medical record review at entry with a lead-in period (<28 days) and repeated measures will occur every three cycles. Changes occurring within 12 weeks of study initiation will be ignored in the absence of compelling evidence of disease progression. Response or progression of pain will be confirmed through repeat assessments separately by at least three weeks. Quality of life measured by the FACT-G, FACIT-Fatigue, QLQ-C30, EPIC-26, and EQ5D will be assessed every 3 cycles.

12.0 STATISTICAL CONSIDERATIONS

12.1 Endpoints

Our primary endpoint is OS. Secondary endpoints include PFS, pain, opiate use, cancer-related fatigue, symptomatic SSE, and QOL-adjusted OS. OS will be measured from the date of randomisation to date of death due to any cause.

12.2 Power and Sample Size for Primary Endpoint

This is a 1:1 randomised controlled trial in men with MCRPC. Registered and eligible participants will be

randomised with equal probability to one of two intervention regimens: supervised exercise for 12 cycles tapering to self-management for 12 cycles with psychosocial support or psychosocial support alone. We will stratify by whether the men are on active therapy or not at the time of registration (yes/no) and study site. A total of 866 men will enrol in this study to ensure at least 412 men evaluable for OS in each arm.

Null hypothesis (H_0)= There is no difference in OS between patients randomised to the exercise intervention plus psychosocial support vs psychosocial support alone.

Alternate hypothesis (H_A) = There is a difference in OS between patients randomised to the exercise intervention plus psychosocial support vs psychosocial support alone.

Considering a total enrolment period of 36-months and minimum 36 months follow-up for each patient after enrolment; assuming survival time follows an exponential distribution; and assuming a median OS survival of 33.5 months in the control arm, the sample size required to detect a hazard ratio (HR) of 0.78 with 80% power at significance level of 0.05 is 824, 412 men in each arm. Accounting for up to 5% of patients with missing data on OS, we aim to enrol 866 men. If we consider non-compliance of 10% in the intervention arm, which equates to 371 patients in the intervention arm who are compliant, this provides 77.7% power to detect an HR of 0.78, when comparing the 371 compliant patients with the 412 patients in the control arm at the significance level of 0.05.

12.3 Data Analysis

Demographic and baseline characteristics will be summarized across the stratification factors, within each arm and overall. In general, frequency distribution and percentage will be used to summarize categorical measurements, while mean (with standard deviation) and median (with range) will be used to describe symmetric and skewed continuous measurements, respectively.

12.4 Analysis of Primary Endpoint

The primary endpoint for the study is OS (defined in Section 10). An intent-to-treat approach will be used to analyse OS. Patients alive at the end of follow-up will be censored on the date of last contact (or, if no contact after the baseline visit, at the date of randomisation + 1 day). Kaplan-Meier methods will be used to estimate the median OS for each treatment arm as well as the 1-year, 2-year, and 3-year OS rates and corresponding 95% confidence intervals. A two-sided log-rank test, stratified by treatment status (on treatment Y/N) and study site, will be used to assess the effect of the intervention. Un-stratified log-rank tests will be examined as sensitivity analyses. Cox proportional-hazard regression models will be used to estimate the hazard ratio and its 95% confidence interval to quantify the effect of the intervention on OS, adjusting for stratification factor(s). First, the base model will be evaluated and then other potential confounding factors will be considered. We will also conduct secondary analyses with consideration for non-compliance and the number of supervised sessions completed.

12.5 Analysis of Secondary Endpoint: Progression-free Survival

PFS will be defined as the time from randomisation to the date of disease progression (defined in Section 11) + 1 day. Patients who have not progressed at the time of the analysis will be censored on the last date of contact OR death, whichever comes first. Patients with no data after randomisation will be censored on the day of randomisation + 1 day. An intent-to-treat approach will be used to analyse PFS. A two-sided log-rank test, stratified by treatment status at registration, will be used to assess the effect of the intervention. Kaplan-Meier methods will be used to estimate median PFS for each treatment arm and the 1-year, 2-year, and 3-year PFS rates and corresponding 95% confidence intervals. Cox proportional-hazard models will be used to assess the magnitude of the effect of the intervention, adjusting for stratification factors and other potential confounding factors.

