10.0 PRIMARY ENDPOINT CRITERIA FOR OVERALL SURVIVAL

Patients will be followed for death a minimum of 36 months after randomisation. Overall survival will be measured from the time of randomisation until death. Medical records and death certificates will be reviewed every 6 months to obtain survival status. Country-specific mortality status databases will also be searched annually; cause of death will be determined through review of medical and death records. Patients will be contacted once a year, and follow up with next of kin then alternate contact, if needed, if we do not hear from them.

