11.0 SECONDARY ENDPOINTS

11.1 Disease progression

Data on disease progression will be obtained through review of patient medical records each cycle. Progression will be determined by the treating physician, and may include any of the following, based on PCWG-3 and RECIST 1.1 criteria:

- Bone scan: Appearance of ≥ 2 new lesions on bone scan, if bone scan >12 weeks after randomisation
- CT/MRI: $\geq 20\%$ increase in the sum of diameters, taking the reference as the smallest sum on study. In addition to the relative increase by 20%, the sum must also demonstrate an absolute increase >5 mm. OR The appearance of one or more new lesions. OR Unequivocal progression of baseline unmeasurable lesions (see further details below). If the patient has measurable disease, there must be overall worsening in non-measurable disease such that the overall tumour burden has increased substantially. The designation of disease progression solely on the basis of change in non-measurable disease in the face of stable disease or partial response of the measurable disease is extremely rare.
- Development of an indication for initiating a therapy for MCRPC after randomisation, including, but not limited to, abiraterone, enzalutamide, chemotherapy, or radiation therapy.
- Symptomatic-skeletal related event (SSE).

Progression free survival will be measured from randomisation until the first of the following: first CT or bone scan documenting disease progression, initiation of a new therapy for MCRPC (clinical progression), or first occurrence of a SSE.

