12.6 Analysis of Secondary Endpoint: Symptomatic skeletal-related events (SSE)

Time to first occurrence of SSE will be defined as the time from randomisation to documentation of any of the following (whichever occurs first) + 1 day:

- Use of external beam radiation therapy to relieve bone pain
- Occurrence of new symptomatic pathological bone fractures that may be vertebral or non-vertebral. Asymptomatic compression fractures detected by radiology review only will not be considered a SSE.
- Spinal cord compression
- Change in antineoplastic therapy to treat bone pain
- Surgical intervention to treat bone pain

Adverse event, concomitant medication, concomitant treatment, or survival follow-up CRFs and the participant's medical record will be the source of these findings and presented as categorical data. Patients who do not experience a SSE will be censored on the date on which they were last known to be event-free. Patients with no data after randomisation will be censored at the date of randomisation + 1 day. The Kaplan-Meier method will be used to estimate the median time to SSE for each group and a log-rank test will be used to determine if there is a statistically significant difference in the time to SSE between the two groups. Cox-proportional hazard regression will be used to estimate the magnitude of the difference between groups and adjust for stratification factors and possible confounding factors.

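### PFS is censored at an undefined last contact rather than the last date a man was known to be progression-free, so unassessed time may count as progression-free

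*Combined protocol and SAP*

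**What the plan says.** Section 12.5 states: "Patients who have not progressed at the time of the analysis will be censored on the last date of contact". In full, the rule is that such men "will be censored on the last date of contact OR death, whichever comes first". Its only other censoring provision is "Patients with no data after randomisation will be censored on the day of randomisation + 1 day", which covers men with no data at all and not men who are in contact but unassessed. The plan does not define contact for this purpose and names no sensitivity analysis on PFS censoring.

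Section 11.1 ends PFS at the earliest of "first CT or bone scan documenting disease progression, initiation of a new therapy for MCRPC (clinical progression), or first occurrence of a SSE".

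Section 12.6 handles skeletal events (SSE) differently: "Patients who do not experience a SSE will be censored on the date on which they were last known to be event-free".

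Section 12.4 uses last contact for overall survival: "Patients alive at the end of follow-up will be censored on the date of last contact".

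On ascertainment, Section 11.1 says "Data on disease progression will be obtained through review of patient medical records each cycle". Table 1 marks disease progression only at Cycles 6, 12, 18 and 24 and then twice yearly, and Section 5.5.12 repeats the twice-yearly schedule. Table 1 has no row for CT or bone scans.

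On contacts, Table 1 footnotes 14 and 15 provide for adverse-event and medication reviews each month, in person or by phone. Section 10 adds: "Patients will be contacted once a year, and follow up with next of kin then alternate contact".

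**The concern.** Last contact suits overall survival, because a contact establishes that the man is alive. It does not by itself establish that he has not progressed. A survey or a relative's reply cannot show that a scan is clear. A monthly phone review can reveal a new therapy or a skeletal event, but not scan progression.

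If the last contact is later than the last informative assessment, the man stays in the risk set over an interval in which an event could not have been recorded. Kaplan-Meier estimates are then too high wherever progression occurred in that interval and was never captured. Section 12.5 plans to report median PFS and the 1-, 2- and 3-year rates, so these are the exposed figures.

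SSE is itself a PFS component. The two sections can therefore censor the same man on different dates for the component and for the composite that contains it.

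**Working it through.** **Plan's own figure.** There is none to reproduce. The plan gives no PFS median, hazard ratio, event count or power.

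**How long the gap can be while reviews run to schedule.**
- Under Section 11.1 (record review each cycle), the last contact is at most about one cycle, 28 days, after the last review.
- Under Table 1 (every 6 cycles, 6 × 28 = 168 days), a man contacted monthly can have a last contact up to 5 × 28 = 140 days after his last progression review.
- In follow-up, review is twice yearly and survey contact yearly. Reviews performed as planned are then the more frequent of the two. A long gap arises only if review stops while contact goes on.

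**Illustration of the effect on rates.** Every input is assumed.
- Progression time is exponential with a 14-month median: λ = ln 2 / 14 = 0.0495 per month.
- A fraction f of men (5% or 10%) stop being assessed at a time U, uniform on 0 to 24 months and unrelated to progression. They stay in contact past month 36, and no progression after U is captured.

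Under last-contact censoring the estimated curve is

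S(t) = (1 − f)·exp(−λt) + f·E[exp(−λ·min(U, t))].

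For t ≥ 24, the expectation is (1 − exp(−24λ)) / (24λ) = (1 − 0.3048) / 1.1883 = 0.5851.

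For t = 12, it is [(1 − 0.5520)/λ + 12 × 0.5520] / 24 = 0.6530.

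With f = 10%:
- 12 months: 0.9 × 0.5520 + 0.1 × 0.6530 = 0.562
- 24 months: 0.9 × 0.3048 + 0.1 × 0.5851 = 0.333
- 36 months: 0.9 × 0.1682 + 0.1 × 0.5851 = 0.210

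| | True | f = 5% | f = 10% |
|---|---|---|---|
| 12-month PFS | 55.2% | 55.7% | 56.2% |
| 24-month PFS | 30.5% | 31.9% | 33.3% |
| 36-month PFS | 16.8% | 18.9% | 21.0% |
| Median (months) | 14.0 | 14.3 | 14.6 |

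Censoring these men at U instead recovers the true column, because U is taken as unrelated to progression.

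**A second illustration, including the hazard ratio.** This was a simulation of 200,000 men split 1:1 with a true hazard ratio of 1.0. The median was 10, 16 or 22 months. Each year 10% or 20% of men stopped being assessed, and contact continued for 6 or 12 months longer.
- Last-assessment censoring recovers the true medians and a hazard ratio of about 1.0.
- Last-contact censoring overstates the median by about 4% to 22%. For a true median of 16 months, 2-year PFS rises from 0.35 to between 0.38 and 0.43.
- With the same assessment loss in both arms, the hazard ratio stays near 1.0.
- With 10% loss a year in one arm and 20% in the other, it moves to about 0.94–0.95 or 1.05 (6-month gap), or to about 0.90–0.91 or 1.10–1.11 (12-month gap). The direction depends on which arm loses more.

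**The case against.** The strongest reply is that planned data collection already covers most of the gap. Supervised sessions record new adverse events and medication changes (Sections 5.5.5 to 5.5.7), and both arms have the monthly reviews through Cycle 24. These contacts inform two of the three PFS components, new therapy and skeletal events. It would be wrong to say that an exercise session carries no progression information. Under Section 11.1 the unreviewed interval is about one cycle at most. If records are complete to the last contact, the rules in 12.5 and 12.6 give nearly the same date. At the assumed 14-month median, about 66% of progressions fall before Cycle 24 Day 1 (24 × 28 = 672 days, 22.1 months), while monthly contact is running. All of this stands and limits the size.

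It does not remove the point. Scan progression is not visible at these contacts. Section 11.1 and Table 1 disagree on the review interval, so the plan cannot rely on the shorter one. After Cycle 24 the yearly and proxy contacts say nothing reliable about progression.

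A reader might also infer that more frequent contact in the supervised arm biases the comparison. The documents do not support that. Three supervised sessions a week is the Cycle 0 schedule only; supervision falls to two, then one a week, then about one per cycle from Cycle 12. With at least monthly contact in both arms through Cycle 24 and the same follow-up schedule afterwards, scheduled frequency moves the last-contact date by less than about 28 days between arms.

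**Conclusion.** The point holds as a defect in a stated rule: PFS rates **could** be overstated where unassessed time exists and progression within it is not captured. A reader might go further and say that they **are** overstated. That does not follow, because complete record review would make the two candidate dates nearly coincide.

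The size cannot be derived from the documents. In the first illustration the excess is 1.4 to 2.8 percentage points at 24 months, 2.1 to 4.2 at 36 months, and 1.0 or less at 12 months. That model is close to a worst case for the men concerned, since they stay in contact past month 36 with nothing captured. The simulation assumes loss of assessment in more men but for shorter gaps, and gives larger shifts in the median.

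Bias in the hazard ratio would need unequal assessment loss between arms. Its sign is unknown, and nothing in the documents establishes it. PFS is a secondary endpoint, and the overall survival analysis is unaffected. How the same sentence treats deaths without progression is a separate question, not assessed here.

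**What to change.** - In Section 12.5, censor PFS at the last date on which imaging or medical-record review documented no progression, in line with Section 12.6.
- Reconcile the review interval in Section 11.1 with Table 1, so that this date is defined for every man.
- Keep last-contact censoring as a named sensitivity analysis.
- Settle the wording before outcomes by arm are seen.

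The cost is a change of analysis wording and a check that the case report form captures the review date. Table 1 footnote 9 already requires record review with confirmation by the site investigator, so no new patient assessments are needed. Reported PFS rates may come out slightly lower.

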1.2 Potential mechanisms of exercise influencing prostate cancer tumour biology

Potential mechanisms by which exercise may lower risk of prostate cancer progression, the incidence and progression of comorbidities, treatment side effects, and overall death among men with advanced prostate cancer include:

- 1) Endocrine - Exercise influences all hormonal systems in the body with key hormones relevant to prostate cancer being testosterone, growth hormone, and insulin-like growth factor-1 (IGF-I). The androgen receptor and its transactivation by ligand are one of the most important determinants of prostate cancer progression. Measurements of serum androgens provide an important biomarker for effectiveness of androgen deprivation and prostate cancer progression. Current studies are inconclusive as to the effects of exercise on serum androgen levels.⁸⁻¹¹ In part, these studies are limited by low patient numbers and inadequate methods for measuring testosterone levels in the low ranges seen in men on androgen deprivation therapy.¹² This is especially true with the newer cyp17 inhibitors, such as Abiraterone.
- 2) Immune System, Inflammation, and Cytokines – High levels of inflammatory biomarkers are associated with an increased risk of prostate cancer-specific mortality,¹³ and exercise is known to lower levels of circulating inflammatory biomarkers (e.g., interleukin-6 (IL-6)) in elderly populations.¹⁴ In addition, exercise may enhance natural killer cell cytotoxicity and immune surveillance, improving immune defence against prostate cancer. Further, adipokines may also have pro- or anti-oncogenic roles in angiogenesis and cell proliferation. For example, adiponectin has anti-inflammatory effects and its serum concentration is inversely correlated with adiposity.¹⁵ Resistin is associated with insulin resistance through AMP kinase down-regulation. It up-regulates pro-inflammatory cytokines (IL-6, tumour necrosis factor alpha (TNF α)) which act via the nuclear factor kappa-light-chain-enhancer of

[figure not shown]

Figure 1. Duration of vigorous physical activity after diagnosis of non-metastatic prostate cancer and risk of prostate cancer recurrence and mortality in two distinct cohorts. Error bars represent the upper bound of the 95% confidence interval ([name] et al, *J Clin Oncol*, 2011; Richman EL et al. *Cancer Res* 2011).

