13.1 Definitions

13.1.1 Clinical Adverse Events (AE)

A clinical adverse event is any unfavourable or unintended sign, symptom, or disease temporally associated with the study intervention and occurring in a patient assigned to the intervention. All AEs reported from the date of informed consent until 28 days after the Off-Study visit will be considered. AEs are assessed by the exercise physiologist, trainer, etc. at on-site exercise visits and in all subjects (in person or by phone) on a monthly basis. This includes adverse clinical or laboratory findings, illness, or an exacerbation or progression of a disease/condition present at baseline. A list of standard questions will be used to assess any AEs, provided in the SOM.

In this trial, the study intervention is defined as supervised aerobic and resistance exercise. All potential participants will be screened via their medical charts as well as through in-person assessments to assess cardiovascular contraindications to exercise. Our multi-gated comprehensive approach should systematically identify and screen out any individual for whom this study is contraindicated.

However, rare but serious AEs are possible. Those that may occur during either cardiopulmonary exercise testing (CPET) or exercise training include myocardial infarction (heart attack), stroke, unconsciousness or other serious injury.

- Events during a CPET are rare (<1/100,000 in well individuals and 1/10,000 in sick individuals). A trained health professional (e.g. medical staff and exercise physiologist) will monitor the exercise test in a location staffed by physicians, in the rare event that such an event occurs.
- Similar to a CPET, exercise training may cause temporary risks of an adverse cardiovascular event, such as a heart attack. The CPET with ECG-monitoring that must be completed prior to randomisation will ensure that all randomised participants are healthy enough to engage in exercise training.

Absolute and relative indications for stopping exercise (both testing and training) are provided in [Table 5](#). In the event of a participant presenting with any of the below symptoms exercise should be stopped.

Table 5. Indicators for Stopping Exercise

Absolute indications for Stopping Exercise:

- Suspicion of a myocardial infarction or acute myocardial infarction (heart attack)
- Onset of moderate-to-severe angina (chest pain)

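### Progression-free survival is defined without death as an event and censors at death, so the planned PFS medians and yearly rates describe time to progression

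*Combined protocol and SAP*

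**What the plan says.** Section 11.1 sets out the endpoint: "Progression free survival will be measured from randomisation until the first of the following: first CT or bone scan documenting disease progression", then "initiation of a new therapy for MCRPC (clinical progression), or first occurrence of a SSE". The list stops there.

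Section 12.5 refers back to it: "PFS will be defined as the time from randomisation to the date of disease progression (defined in Section 11) + 1 day". Its censoring rule is that men who have not progressed by the analysis "will be censored on the last date of contact OR death, whichever comes first". The same section plans a stratified log-rank test, Cox models, Kaplan-Meier medians by arm and "the 1-year, 2-year, and 3-year PFS rates and corresponding 95% confidence intervals", all under the name PFS.

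The secondary objective in Section 2.2 is a comparison of progression-free survival. Nowhere do the documents count death as a PFS event, and no competing-risk or sensitivity analysis is given for PFS. Death from any cause is an event only for overall survival (OS; Sections 10 and 12.1).

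**The concern.** A PFS rate is read as the proportion of men alive and free of progression. With death censored, a man who dies without an event leaves the risk set as though he could still progress later. The resulting curve is not the probability of being alive and progression-free. Nor is its complement the cumulative incidence of progression, because a death rules out later progression.

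The protocol itself gives reasons to care about deaths before progression. Section 1.2 lists, among the outcomes exercise may improve, "the incidence and progression of comorbidities, treatment side effects, and overall death among men with advanced prostate cancer". Section 13.1.1 warns that "exercise training may cause temporary risks of an adverse cardiovascular event, such as a heart attack". A benefit or harm confined to deaths before progression would not show in this endpoint. Such deaths do count in OS, but there they are mixed with deaths after progression.

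**Working it through.** **1. Reading the text.** Sections 11.1 and 12.5 agree with each other, so this is not a drafting conflict. The mismatch lies between the endpoint's name and objective and its operating definition. Last contact cannot follow death, so the censoring rule removes a man who dies event-free at his last contact or at his death. Either way no event is counted.

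**2. Inputs.** The documents state no PFS median, rate, event count or power, so there is no figure of the plan's to reproduce. Everything below is illustrative and assumes:

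- constant, independent hazards: hp for progression as Section 11.1 defines it, and hd for death without progression;
- d = hd/(hp + hd), the share of first events that are deaths, set at 5%, 10% and 20%;
- M, the median that the planned analysis would report, set at 12, 18 and 24 months, so hp = ln 2/M.

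**3. Median.** The planned analysis estimates ln 2/hp. With death counted, the median is ln 2/(hp + hd). The ratio is (hp + hd)/hp = 1/(1 − d):

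- d = 5%: 1/0.95 = 1.053
- d = 10%: 1/0.90 = 1.111
- d = 20%: 1/0.80 = 1.250

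**4. Rates.** The gap at time t is exp(−hp·t) − exp(−(hp + hd)·t). Over M = 12, 18, 24 and t = 12, 24, 36 months it spans:

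- d = 5%: 1.3 to 1.9 percentage points
- d = 10%: 2.6 to 3.9 points
- d = 20%: 5.1 to 8.2 points

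Worked case, M = 18 and d = 10%: the median with death counted is 18 × 0.90 = 16.2 months. At 24 months the planned rate is exp(−24 ln 2/18) = 39.7%. With death counted it is exp(−24 ln 2/16.2) = 35.8%, a gap of 3.9 points. A Kaplan-Meier simulation gave 18.0 against 16.2 months and 39.6% against 35.8%.

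**5. Treatment contrast.** If exercise changes only deaths before progression, the planned analysis has a hazard ratio (HR) of 1.00, while the HR with death counted is (1 − d) + HR·d, d being the control-arm share:

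| d | death HR 0.78 | death HR 1/0.78 |
|---|---|---|
| 5% | 0.989 | 1.014 |
| 10% | 0.978 | 1.028 |
| 20% | 0.956 | 1.056 |

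The 0.78 is borrowed from the OS design in Section 12.2; its reciprocal is an assumed harm of matching size. If exercise acts equally on progression and on these deaths, the HR is the same under either definition.

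**The case against.** The definition is written out openly and the two sections agree, so this can be called a labelling matter that renaming would largely cure. PFS is secondary, with no power calculation or decision rule attached, and the HR barely moves. Fatal harm would also be seen elsewhere: on-study deaths are reported under Sections 13.1.2 and 13.5.2, adverse events are compared between arms under Section 13.7, and cause of death is centrally reviewed (Table 1, footnote 9). Section 13.1.1 calls serious exercise events rare, and the cardiac exclusions in Section 3.2 make them less likely still.

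These points limit the consequences, and they stand. They do not make the reported medians and rates correct for the quantity they are named after.

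The rate gaps do depend on the assumed median. With d = 10%, a 9-month median gives a 3-year gap of about 1.7 points and a 6-month median about 0.6, both below the range above. Short medians are plausible, because untreated men are eligible and starting a new therapy is an event. The median ratio 1/(1 − d) does not depend on M. Timing matters too: a death at month 30 leaves the 1- and 2-year estimates unchanged.

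The date of last progression review also needs a definition. Section 11.1 speaks of record review each cycle, whereas Table 1 shows progression status at cycles 6, 12, 18 and 24 and then twice yearly.

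**Conclusion.** The concern holds. What the plan calls PFS is time to progression with deaths censored, and its medians and yearly rates will overstate survival free of progression to the extent that men die event-free before the time point. Under constant, independent hazards the median is overstated by 5%, 11% or 25% for death shares of 5%, 10% or 20%. The rates are overstated by about 1 to 8 percentage points for reported medians of 12 to 24 months.

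The death shares and medians are assumptions. Entry limited to ECOG 0–1 and low or intermediate Halabi risk, and the counting of new therapy and skeletal events, favour the lower end. The between-arm comparison changes little and the primary OS conclusion does not change. It should be corrected because the published figures would otherwise carry a name that does not describe them.

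**What to change.** In Sections 11.1 and 12.5, define PFS as time from randomisation to the first of imaging progression, new therapy for the disease, symptomatic skeletal event, or death from any cause. Remove death from the censoring rule. Censor men alive without an event at their last progression review, since last contact can fall later than that review. Section 12.6 already follows this principle for skeletal events, censoring at the date a man was last known to be free of one. If the present endpoint is also wanted, call it time to progression and analyse it with death as a competing event.

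Adding death needs only wording in two sections, because death dates are already collected (Section 10; Table 1, footnote 9). The censoring change also needs one agreed, recorded review date, with Section 11.1 and Table 1 reconciled on how often progression is reviewed.

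The price is somewhat shorter PFS medians and lower rates, and some dilution if exercise acts only on progression. With a progression HR of 0.78, the composite HR is 0.78(1 − d) + d, which is 0.791, 0.802 or 0.824 at death shares of 5%, 10% or 20%.
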